3.8.5 Other Safety Evaluations

Additional data collected throughout the study include important protocol deviations, screen failure data, significant findings in medical history and physical exam, vital signs, chest X-ray, oxygenation status, oxygen log, microbiology data, antibiotics, and concomitant medications through 49 days post dose.

Data listings will be provided and no formal analyses will be conducted on these data. Upon review of the listings, additional summary tables may be generated as appropriate.

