#### Vital Signs

Vital signs (temperature, blood pressure, pulse rate, and respiratory rate) will be obtained as indicated in Table 4.2.1-1, Table 4.2.2-1 and Table 4.2.2-2.

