## 4.5.1.3 Monitoring of Dose Administration

Subjects will be monitored with assessment of vital signs (temperature, respiration rate, heart rate, and blood pressure). Vital signs will be obtained on the day of dosing prior to the start of infusion (2 recordings of blood pressure and pulse rate, 5 minutes apart), every  $30 (\pm 5)$  minutes during investigational product infusion, at completion of infusion ( $\pm 5$  minutes), every  $30 (\pm 5)$  minutes after completion of infusion for 2 hours, and 24 hours ( $\pm 30$  minutes) after completion of infusion.

[figure not shown]
As with any antibody, allergic reactions to dose administration are possible. Therefore, appropriate drugs and medical equipment to treat acute anaphylactic reactions must be immediately available, and study personnel must be trained to recognise and treat anaphylaxis.

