# 5.3.2 Hypersensitivity (Including Anaphylaxis) and Infusion related Reactions

Administration of polyclonal immunoglobulin preparations and mAbs have been associated with hypersensitivity (including anaphylaxis) and infusion related reactions that occur during or after dosing. A hypersensitivity reaction is defined as an acute onset of an illness with involvement of the skin, mucosal tissue, or both, during infusion of investigational product (but does not meet the definition of anaphylaxis). Anaphylaxis is an acute onset, potentially fatal, systemic allergic reaction that is distinct from simple allergic reactions (eg, rash, pruritus) because of the simultaneous involvement of several organ systems (Sampson et al, 2006). An infusion related reaction is defined as any other reaction (other than hypersensitivity or anaphylaxis) occurring during infusion of investigational product or felt to be temporally related to the infusion.

Anaphylaxis and infusion related reactions have some common manifestations and may be difficult to distinguish from each other. Infusion related reactions typically develop within

30 minutes to 2 hours after the initiation of first drug infusion. However, though less frequent, infusion related reactions can occur later on within first 24 hours from the start of infusion, and are less common following subsequent exposures. Infusion related reactions may manifest with single or multiple signs and symptoms. Most of them are mild in intensity, but severe and even fatal reactions have been reported. Unlike infusion related reaction, anaphylaxis is a rare event, usually occurring after subsequent exposure to antigen, and it is most commonly accompanied by severe systemic skin and/or mucosal reactions. A full definition of anaphylaxis is provided in Appendix 3.

Signs and symptoms of hypersensitivity (including anaphylaxis) and infusion related reactions include, but are not limited to, fever, chills, rigors, myalgia, weakness, flushing, sweating, headache, dizziness, lightheadedness, syncope, seizure, anxiety, nasal congestion, rhinitis, sneezing, oropharyngeal or laryngeal edema, bronchospasm, dyspnea, tachypnea, cyanosis, respiratory arrest, tachycardia, hypotension, arrhythmia, chest pain, ischemia or infarction, cardiac arrest, flushing, erythema, pruritus, urticaria, angioedema, maculopapular rash, nausea, vomiting, cramping, and diarrhea (Kang and Saif, 2007).

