# Appendix 3 National Institute of Allergy and Infectious Diseases and Food, Allergy and Anaphylaxis Network Guidance for Anaphylaxis Diagnosis

NIAID and FAAN define anaphylaxis as a serious allergic reaction that is rapid in onset and may cause death. They recognise 3 categories of anaphylaxis, with criteria designated to capture from 80% of cases (category 1) to > 95% of all cases of anaphylaxis (for all 3 categories).

1. Acute onset of an illness (minutes to several hours) with involvement of the skin, mucosal tissue, or both (eg, generalised hives, pruritus or flushing, swollen lips-tongue-uvula)

AND AT LEAST ONE OF THE FOLLOWING

- a. Respiratory compromise (eg, dyspnea, wheeze-bronchospasm, stridor, reduced peak expiratory flow [PEF], hypoxemia)
- b. Reduced blood pressure (BP) or associated symptoms of end-organ dysfunction (eg, hypotonia [collapse], syncope, incontinence)
- 2. Two or more of the following that occur rapidly after exposure to a likely allergen for that patient (minutes to several hours):
  - a. Involvement of the skin-mucosal tissue (eg, generalised hives, itch-flush, swollen lips-tongue-uvula)
  - b. Respiratory compromise (eg, dyspnea, wheeze-bronchospasm, stridor, reduced PEF, hypoxemia)
  - c. Reduced BP or associated symptoms (eg, hypotonia [collapse], syncope, incontinence)
  - d. Persistent gastrointestinal symptoms (eg, crampy abdominal pain, vomiting)
- 3. Reduced BP after exposure to known allergen for that patient (minutes to several hours):
  - a. Infants and children: low systolic BP (age specific) or greater than 30% decrease in systolic BP
  - b. Adults: systolic BP of less than 90 mm Hg or greater than 30% decrease from that person's baseline

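### The SAP pre-specifies no by-arm summary of the vital signs measured closely around the infusion, so changes that no investigator records as an adverse event reach no planned table

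*SAP*

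**What the plan says.** Infusion-related reactions and hypersensitivity, including anaphylaxis, are adverse events of special interest (AESIs; protocol 4.8.4.1). AESIs are part of the primary safety endpoint (protocol 2.2.1).

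Protocol 4.5.1.3, repeated in a footnote to Table 4.2.2-1, sets the vital-sign schedule:

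- before the infusion, with blood pressure and pulse taken twice;
- every 30 (± 5) "minutes during investigational product infusion, at completion of infusion";
- every 30 (± 5) "minutes after completion of infusion for 2 hours, and 24 hours" after completion.

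Protocol 5.3.2 puts the usual onset of an infusion reaction at 30 minutes to 2 hours after the start and adds that "infusion related reactions can occur later on within first 24 hours from the start of infusion". Its list of signs includes fever, tachycardia, hypotension and tachypnoea, so each of the four measured vital signs bears on a reaction.

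SAP 3.8.5 groups vital signs with protocol deviations, screen failures and concomitant medications: "Data listings will be provided and no formal analyses will be conducted on these data". The next sentence allows further summary tables after the listings have been reviewed. It does not say which tables, or that they would be by arm. Protocol 4.8.4 covers adverse events and laboratory data only. Laboratory data receive more in SAP 3.8.4: observed values, change from baseline, toxicity grades and grade shifts, by treatment group.

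**The concern.** The schedule looks designed to catch reactions to the infusion, yet the plan makes no comparison of what it measures. The planned by-arm information on reactions comes from events that investigators recognised and recorded.

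That recognition is harder here than in most trials. Subjects are intubated at entry (inclusion criterion 4), so many cannot report headache, dizziness, nausea or anxiety, which are also in the 5.3.2 list. The remaining signs are common in critical illness, and a modest or brief change may be seen as part of the patient's course and not recorded. The placebo arm supplies the background rate needed to judge such changes, but only if measured values are set side by side by arm. Tables chosen after reading the listings would be data-driven and harder to interpret.

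**Working it through.** The plan gives no figure to reproduce on this point. The check has four steps.

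**1. How much is collected.** For an infusion of *h* hours, blood pressure and pulse readings per subject are 2 (before) + (2*h* − 1) (during) + 1 (end) + 4 (next 2 hours) + 1 (at 24 hours) = 2*h* + 7. The minimum infusion time is redacted, so *h* is an assumption. Protocol 4.5.1.2 requires the medical monitor to be notified above 8 hours (12 after a dose adjustment).

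| Assumed duration | Readings per subject |
|---|---|
| 1 hour | 9 |
| 2 hours | 11 |
| 4 hours | 15 |
| 8 hours | 23 |

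All but the 24-hour reading fall between pre-dose and 2 hours after completion. Leaving out in-infusion readings and counting the pre-infusion pair as one time point gives 1 + 1 + 4 + 1 = 7 time points, and 7 × 286 = 2,002 sets.

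**2. What reaches a planned by-arm table.**

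| Item | Planned handling |
|---|---|
| Sign recorded as an adverse event, any attribution | By arm (SAP 3.8.1) |
| Event recorded as a reaction (AESI) | By arm, plus duration and time to onset (SAP 3.8.2) |
| Laboratory values | By arm, with change from baseline (SAP 3.8.4) |
| Measured vital sign, no adverse event recorded | Listing; optional tables after review (SAP 3.8.5) |

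Protocol 5.1 defines an adverse event without regard to causality. Hypotension blamed on sepsis still counts if it is recorded. Only the last row is missing from the planned tables.

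**3. Direction of the effect.** Suppose a fraction *f* of true changes is recorded, the same in both arms because assessment is blinded (protocol 4.6.2). The expected difference then shrinks from *p*₁ − *p*₀ to *f*(*p*₁ − *p*₀), while the ratio stays at *p*₁/*p*₀. A real difference becomes harder to see, but neither arm is favoured.

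**4. What a by-arm count would deliver.** With 143 per arm and the same rate *p* in both, the 95% half-width for the difference is 1.96 × √(2*p*(1 − *p*)/143). The rates below are assumed.

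| *p* | Half-width (percentage points) |
|---|---|
| 5% | 5.1 |
| 10% | 7.0 |
| 20% | 9.3 |
| 30% | 10.6 |

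That is coarse but informative about a large effect.

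**The case against.** A reader might infer that vital signs are only ever listed, and that objective hypotension, fever or tachycardia is never compared between arms. The documents do not support that. SAP 3.8.5 allows summary tables after review, and any such sign recorded as an adverse event is compared by arm. A reader might also infer that events put down to ICU illness drop out. They do not: attribution decides only whether an event carries the infusion-reaction label.

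Other safeguards exist. Protocol 3.1.3 has the data monitoring committee follow how often and how severely reactions occur, and SAP 3.4.3 summarises infusion interruptions. Table details sit in a separate Statistical Programming Plan (SAP 1), which is not available. Parts of the statistical sections are redacted, and nothing is inferred from them.

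These points narrow the concern but do not remove it. The optional tables are discretionary, chosen after sight of the data and not stated to be by arm. The other safeguards act on recognised events or stopped infusions. The programming plan gives detail for planned outputs, and for these data the SAP plans listings.

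The harm is also hard to size. If 5% on placebo and 15% on active had a qualifying change, full recording with 143 per arm would give power 0.95 at the SAP's 2-sided alpha of 0.2 (tested one-sided at 0.10), and recording of a quarter would give 0.57. At one-sided 0.025 the figures are 0.82 and 0.25. Every rate and recording fraction here is assumed, none has a source in the documents, and the plan sets out no specific test for safety data. The point should not rest on these figures.

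**Conclusion.** The point holds as a limited gap. No by-arm summary of measured vital signs is pre-specified, although they are collected closely over the window in which the protocol expects reactions, and reactions belong to the primary safety endpoint. What can be missed is a change in blood pressure, pulse, respiratory rate or temperature that no investigator recorded as an adverse event.

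This is a loss of sensitivity. Calling it no bias rests on the blind holding, so that under-recording is similar in both arms. Efficacy, sample size and error rates are unaffected. Its size in events is unknown; all that can be counted is the roughly 2,000 sets of readings, outside the infusion itself, with no planned summary. It is a worthwhile, inexpensive improvement and not a fault that threatens the trial.

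**What to change.** In SAP 3.8.5, take vital signs out of the listings-only group. For the As-treated Population, by treatment group:

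1. Summarise observed values and change from the last pre-infusion value at each scheduled time through 24 hours after completion, as SAP 3.8.4 already does for laboratory data.
2. Tabulate subjects with at least one value crossing a threshold fixed before unblinding, as counts and percentages, with the difference from placebo and its confidence interval. Keep this descriptive, with no formal test, and include subjects whether or not an adverse event was recorded.

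Thresholds already in the protocol can serve as table categories only, not as diagnostic or management rules. Appendix 3 has "systolic BP of less than 90 mm Hg or greater than 30% decrease from" the person's own baseline. Protocol 4.3.1.4 has temperature > 38°C oral or tympanic, or ≥ 38.3°C core; the two must be kept apart by site of measurement, since applying 38°C to core readings would overcount. Count only new temperature elevations.

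The cost is a paragraph of SAP text and two or three standard tables from data already collected. ICU illness adds a background of threshold crossings and vasopressor use will blunt the blood pressure counts, so read them against placebo and not as absolute rates.

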3.9 Antidrug antibody Response

The number and percentage of subjects who develop anti-MEDI3902 antibodies will be summarized at each visit by treatment group and for MEDI3902 total. Subjects will be excluded from the summary of an individual visit if data to that specific visit are missing. For those with a positive assessment or borderline positive assessment, the ADA titer results will also be summarized. Antidrug antibody values reported as borderline positive (ie, \leq LLOQ), a value equal to LLOQ will be imputed in the summaries. An additional table will summarise the number and percentage of subjects positive for ADA at baseline (ie, ADA prevalence) and positive at any post-baseline time point (ie, ADA incidence). For those with a positive post-

baseline assessment, the percentage who were persistent positive and transient positive will also be presented.

5. Persistent positive is defined as positive at ≥ 2 post-baseline assessments (with ≥ 16 weeks between first and last positive) or positive at last post-baseline assessment.
6. Transient positive is defined as negative at last post-baseline assessment and positive at only one post-baseline assessment or at ≥ 2 post-baseline assessments (with < 16 weeks between first and last positive).

AEs will be summarized by SOC and PT based on MedDRA for subjects with ADA to MEDI3902 at any time post-baseline. The impact of ADA on PK will be included in the PK report as mentioned in Section 3.10.

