## 4.3.6 Anti-drug Antibody Evaluation and Methods

Blood samples will be collected to evaluate ADA responses to MEDI3902 in serum according to the schedule in Table 4.2.2-1. For subjects with a suspected serious *P aeruginosa* infection, blood samples will be collected for ADA evaluation on the day of onset of illness (see Table 4.2.2-2).

Evaluations for ADA will be performed using a set of electrochemiluminescent, solutionphase, bridging immunoassays. Tiered analyses will be performed to include screening, confirmatory, and titer assay components, and positive-negative cutoff points will be employed that were statistically determined from drug-naive validation samples. Samples confirmed positive for ADA may be characterised for neutralising antibody activity.

Redacted
Reda
cted

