#### 4.8.7 Anti-drug Antibody Response

The immunogenic potential of MEDI3902 will be assessed by summarising the number and percentage of subjects who develop detectable ADAs in serum through 49 days postdose. The impact of ADA on PK will be assessed if data allow. Safety data will also be assessed in subjects with ADA.

Reda	
R e	
e	
Redacted	

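### The SAP counts any positive post-baseline ADA result as incident, even in subjects already positive before dosing, and its 16-week persistence rule cannot be met in a 49-day follow-up

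*SAP*

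**What the plan says.** Protocol section 2.2.2 makes serum ADA response through 49 days postdose one of two secondary endpoints. Protocol section 4.8.7 plans to summarise "subjects who develop detectable ADAs in serum through 49 days postdose". SAP section 3.9 opens in the same terms: "The number and percentage of subjects who develop anti-MEDI3902 antibodies will be summarized at each visit".

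SAP 3.9 then adds a table with two items. Prevalence is positivity at baseline. Incidence is being "positive at any post-baseline time point (ie, ADA incidence"). No negative baseline and no rise in titre is required for the second item.

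Among subjects with a positive post-baseline result, "the percentage who were persistent positive and transient positive will also be presented". Persistent means at least two post-baseline positives "with ≥ 16 weeks between first and last positive) or positive at last post-baseline assessment". Transient means negative at the last sample with either a single positive or several positives less than 16 weeks apart. Adverse events are also summarised for subjects with ADA at any post-baseline time.

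Titres are already planned: "For those with a positive assessment or borderline positive assessment, the ADA titer results will also be summarized".

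**The concern.** An incidence should count what arises after dosing. Under SAP 3.9 a subject with unchanged predose reactivity is incident. Neither document defines what it is to develop antibodies, but an unchanged predose positive is not a natural reading of it.

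The same subjects pass into the persistent/transient denominator, and any still positive at the last sample are called persistent. This follows from the incidence rule rather than being a second independent defect, but it changes a second reported figure.

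The 16-week wording raises a smaller issue. It suggests that persistence is judged over a set interval, which the sampling schedule cannot supply.

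At stake are the ADA rates for each arm and for MEDI3902 total, and how durable the response appears to be.

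**Working it through.** **Sampling span.** Protocol Table 4.2.2-1 puts serum ADA at predose, Day 15 (±2), Day 29 (±3) and Day 50 (±4). Protocol section 4.3.6 adds that, for a suspected serious infection, "blood samples will be collected for ADA evaluation on the day of onset of illness"; footnote a of Table 4.2.2-2 covers onsets from Day 2 through Day 29. The required interval is 16 × 7 = 112 days. The longest possible gaps between post-baseline samples are:

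- nominal days: 50 − 15 = 35
- with visit windows: (50 + 4) − (15 − 2) = 41
- with a Day 2 illness-onset sample: (50 + 4) − 2 = 52

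All fall short of 112, so the condition of at least 16 weeks is never true and the condition of less than 16 weeks is always true.

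**What the classes then mean.** Let each of Days 15, 29 and 50 be missing, negative or positive, with at least one sample.

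- All patterns: 3³ − 1 = 26. Without a positive: 2³ − 1 = 7. With a positive: 26 − 7 = 19.
- Last available sample positive (persistent): 9 + 3 + 1 = 13, of which 4 + 2 + 1 = 7 rest on a single positive.
- Last available sample negative (transient): 19 − 13 = 6.
- Deleting the whole two-positive limb changes 0 of 19.
- Adding an onset sample on any of Days 2 to 28 except Day 15 gives 26 × (27 × 2 − 8) = 1,196 patterns with a positive; again 0 change.

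These counts are unweighted and do not estimate numbers of subjects. Deleting only the parenthesis from the persistent definition would not be safe: a subject positive on Days 15 and 29 and negative on Day 50 would then be both persistent and transient.

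**Incidence.** Let *b* be the baseline-positive rate, *r* the share of those who stay positive without a titre rise, and *n* the rate of new positives among baseline-negatives. The documents give none of the three, so all values are assumptions. No baseline-positive subject is assumed to have a titre rise.

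- SAP incidence = *b·r* + (1 − *b*)·*n*
- Treatment-emergent incidence = (1 − *b*)·*n*
- Excess = *b·r*

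For the persistent share in the last column, assume that half of new positives are negative at the last sample and that all carry-overs are positive there: (*b* + (1 − *b*)·*n*/2) / (*b* + (1 − *b*)·*n*). With *n* = 5% and *r* = 1:

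| *b* | SAP incidence | Treatment-emergent | Extra subjects per 143 | Persistent share under SAP |
|---|---|---|---|---|
| 0% | 5.0% | 5.0% | 0 | 50.0% |
| 1% | 5.95% | 4.95% | 1.4 | 58.4% |
| 2% | 6.9% | 4.9% | 2.9 | 64.5% |
| 5% | 9.75% | 4.75% | 7.2 | 75.6% |

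The persistent share among treatment-emergent subjects is 50% in every row. With *r* = 0.5 the excess halves, and SAP incidence is 5.0%, 5.45%, 5.9% and 7.25%. With *n* = 2% and *r* = 1 it is 2.0%, 2.98%, 3.96% and 6.9%.

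**Between arms.** Take *b* = 5% and *r* = 1 in both arms, with *n* = 5% on MEDI3902 and 1% on placebo.

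- SAP: 0.05 + 0.95 × 0.05 = 9.75% against 0.05 + 0.95 × 0.01 = 5.95%; difference 3.8 points, ratio 1.64.
- Treatment-emergent: 4.75% against 0.95%; difference 3.8 points, ratio 5.0.

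**The case against.** The strongest reply is that no material effect has been shown. Baseline positivity may be close to zero: Protocol section 4.1.3 excludes anyone who has previously received a monoclonal antibody, and in Protocol section 4.3.6 "Tiered analyses will be performed to include screening, confirmatory, and titer assay components", with cut-points set on drug-naive samples. The rows above with *r* = 1 are an upper bound. The count per 143 assumes everyone is evaluable; with the planned 20% attrition, 143 × 0.8 ≈ 114, and 7.2 extra subjects become 5.7. The SAP plans no ratio and no test of ADA rates, and the difference between arms is unchanged if carry-over is similar in both, as randomisation makes likely. Prevalence stands in the same table, summaries are by arm, and subject listings are planned. The table shells sit in a separate programming plan and the ADA–PK work in a separate report, neither of which is available here.

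All of this stands as a limit on size. None of it changes the rule. Prevalence and incidence shown as separate totals do not reveal how many subjects are in both, and SAP 3.9 specifies no incidence by baseline status. The arm-level rates and the persistent percentage, which the SAP does plan to report, move whenever there is carry-over. An unknown baseline rate is a reason to fix the definition before unblinding rather than to leave it open.

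It is also fair to say that a titre-rise criterion appears nowhere in the documents, so its value has to be chosen, and that the 16-week point on its own is only one of wording.

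**Conclusion.** The concern holds. SAP 3.9 states an incidence rule that counts unchanged predose positives, contrary to the sense of its own opening sentence and of Protocol 4.8.7, and it carries them into the persistence percentages. The excess in incidence is *b·r*: zero if nobody is positive before dosing, and 5 points at the top of the range shown (*b* = 5%, *r* = 1), where the persistent share would read about 76% instead of 50%. These sizes rest entirely on assumed rates.

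That the 16-week limb is inert is certain from the schedule and rests on no assumed rate. In practice persistent means positive at the last available sample, even on one isolated result, and transient means negative there.

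The consequence is confined to descriptive tables for a secondary endpoint. It should be corrected, but it does not touch the efficacy analysis or power.

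**What to change.** In SAP 3.9:

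- Define ADA incidence as treatment-emergent: negative at baseline and positive afterwards, or positive at baseline with a titre rise of at least a fold fixed in the SAP before unblinding. Take a borderline-positive baseline at the LLOQ, as 3.9 already imputes.
- State the denominator as subjects with a baseline result and at least one post-baseline result.
- Report baseline-positive subjects without that rise on a separate line.
- Base the persistent and transient percentages on treatment-emergent subjects.
- Keep the adverse-event summary for all post-baseline positives and add the treatment-emergent subset.
- Remove the whole two-positive limb from the persistent definition and the less-than-16-weeks condition from the transient one. Relabel the classes as positive or negative at the last post-baseline sample, and show how many subjects rest on a single positive. If the sponsor wants a different persistence interval, it must be one that the schedule can reach.

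The cost is SAP wording and table-shell edits. No visit, sample or assay is added, since the predose sample and titres are already planned. The sponsor has to choose and justify the titre fold, and reported incidence may fall. Removing the 16-week limb moves no subject between classes.
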